	variable	calculated for each of the study cohorts. If
		alive at data cut-off patient censored on last
		visit date with provider/at office

*Appropriate definitions will be provided to the physicians in the CRF, and they will be requested to substantiate by the progress notes and laboratory results.

9.4. Data sources

Providers will complete data abstraction into the eCRF using all structured and unstructured data, including laboratory, pathology, and radiology files from the selected patients' EMR.

9.5. Study size

As no *a priori* hypotheses are specified for this study, a sample size calculation is not applicable. Prior to study start in November 2019, a feasibility assessment of the OPEN database was conducted to understand the number of patients with AML managed or treated by providers within OPEN and specifically the number treated with GLAS post-approval. A total of 30 providers indicated they had treated at least 1 AML patient in the past 2 years. Providers reported treating a total of 320 AML patients deemed ineligible for high intensity induction chemotherapy. Providers were asked to indicate the treatment regimens received by those 386 patients. Feasibility assessment indicated 11 providers prescribed GLAS to 39 patients and 21 providers prescribing VEN to 86 patients. The results of this feasibility were used to generate the proposed samples sizes for this study (**Table 9.5.1**).

Doint actimates	Sample size					
Point estimate:	n=30	n=50	n=100	n=200	n=250	n=300
5%/95% responding to categorical variable	$\pm 7.8\%$	$\pm 6.0\%$	$\pm 4.3\%$	$\pm 3.0\%$	$\pm 2.7\%$	$\pm 2.5\%$
20%/80% responding to categorical variable	± 14.3%	$\pm 11.1\%$	$\pm 7.8\%$	± 5.5%	± 5.0%	$\pm 4.5\%$
30%/70% responding to categorical variable	±16.4%	± 12.7%	$\pm 9.0\%$	$\pm 6.4\%$	± 5.7%	± 5.2%
40%/ 60% responding to categorical variable	± 17.5%	± 13.6%	$\pm 9.6\%$	$\pm 6.8\%$	± 6.1%	$\pm 5.5\%$
50%/ 50% responding to categorical variable	$\pm 17.9\%$	± 13.9%	$\pm 9.8\%$	$\pm 6.9\%$	± 6.2%	± 5.7%

Table 9.5.1 Standard Error around a Point Estimate.

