9. RESEARCH METHODS

9.1. Study design

This study will be conducted through a multi-site medical chart review of AML patients treated at oncology clinics in the US. Providers in the Cardinal Health Oncology Provider Extended Network (OPEN) will be recruited to participate in the patient identification and data abstraction. All study data are secondary data and will have been collected retrospectively from existing clinical data originally collected as part of routine care.

Patient eligibility will be confirmed by the treating physician. Providers will abstract the patient level data necessary to achieve the research objectives into an electronic case report form (eCRF). No protected health information, except for dates of diagnosis, treatment, and outcomes, will be collected. The patients electronic medical record (EMR) will not be shared directly with Cardinal Health or Pfizer.

Two different types of AML patient cohorts will be identified as follows:

• GLAS-based: initiated first-line or later therapy (eg, index therapy) with GLAS+AZA, GLAS+DEC, GLAS+LDAC between 01 December 2018 and 31

PFIZER CONFIDENTIAL

CT24-WI-GL02-RF02 1.0 Non-Interventional Study Protocol Template For Secondary Data Collection Study 15-Aug-2018 Page 17 of 35 December 2019 (allowable combinations include GLAS plus low-dose cytarabine, GLAS plus azacytidine, or GLAS plus decitabine)

• VEN-based: initiated first-line (index) therapy with VEN+AZA, VEN+DEC, VEN+LDAC between 01 December 2018 and 31 December 2019 (allowable combinations including VEN plus low-dose cytarabine, VEN plus azacytidine, or VEN plus decitabine)

The study will be conducted in 5 sequential phases. The total proposed sample size across the 2 treatment arms is 150 patients. Figure 1 illustrates the study period.

Phase 1: Study Concept Feasibility

Cardinal Health Specialty Solutions (CHSS) research operations team, the investigator, will conduct outreach to OPEN inquiring as to the number of physicians who have prescribed GLAS per the study selection criteria. Providers will also be queried regarding their acceptance of the rules and conditions associated with participation in the research study.

Phase 2: eCRF Testing

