A total of 4 community oncologists will review the eCRF and abstract data for the purposes ensuring the requested clinical datapoints are available, the intent of the data point is clear, and the eCRF functions appropriately. Providers who participate in this testing phase are able to participate in further data collection. To test the eCRF providers will select 1 AZA-treated patient and complete data abstraction while Cardinal Health Specialty Solutions (CHSS) research operations team members watch data entry (via screen sharing), respond to questions from the providers, and ask questions of the providers as necessary. No data from this phase will be used in the final analytical dataset. After completion of eCRF testing, revisions to the eCRF will be made as necessary prior to the launch of study data collection.

Phase 3: Study Conduct Feasibility

CHSS will invite 15 providers who have indicated previously treating a patient with GLAS to participate in Phase 3. In Phase 3, each provider will abstract data for 1 GLAS-treated patient, randomly-selected, per the study selection criteria for a total of 15 patients. Providers will abstract data into the eCRF during a web-based, screen-sharing session with a member of the CHSS research operations team. Demographic, clinical, and disease-related characteristics of these patients, treatment patterns, and clinical outcomes will be described. After evaluating these data, Pfizer may elect to discontinue the study and not collect further data for either GLAS- or VEN-treated patients.

Phase 4a: GLAS Data Collection Expansion

Based on the results of Phase 3, Pfizer may elect to continue data collection. In addition, Pfizer may elect to expand data collection to include patients who received a GLAS-based regimen as second-line or greater should sufficient sample sizes of those patients be discovered during Phase 3 when provider enumerate all patient for whom they have prescribed a GLAS-based regimen. CHSS will allow data abstraction for the maximum number of GLAS-treated patients up to the total *a priori* sample size of 150 patients.

PFIZER CONFIDENTIAL

CT24-WI-GL02-RF02 1.0 Non-Interventional Study Protocol Template For Secondary Data Collection Study 15-Aug-2018 Page 18 of 35

Depending upon the number of GLAS-treated patients and the length of follow-up for these patients, Pfizer may elect to discontinue the study and not collect data for the VEN-treated cohort.

Phase 4b: VEN Data Collection

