Should Pfizer elect to proceed with further data collection, CHSS will initiate Phase 4b, which will collect data for VEN-treated patients from those initial providers who participated in Phase 3 data collection. At the end of data collection, summary results for the VEN-treated patients will be provided.

Phase 5: Long-Term Follow-Up

As a retrospective observational study with an index period of 1 year between December 2018 and December 2019, longer follow-up of patients may be required to observed clinical outcomes of interest. As such, at the conclusion of the initial phases of data collection, additional wave(s) of follow-up may occur approximately 4 months later (a maximum of 3 additional updates, Phases 5a-c as applicable). The records of patients who were alive at the time of the initial data collection will be updated. In addition, new patients may be included during the follow-up periods; however, the total sample size is currently set at 150 regardless of when the patient was entered into the study.

Figure 1. Study Period*

*Initial data collection (Phase 3) lasts for 4 weeks. Exact start date of data collection may vary. Subsequent extended follow-ups at Pfizer discretion. Study may be stopped at any time post a data collection point.

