9.7. Data analysis

9.7.1. Analysis overview

Detailed methodology for summary and statistical analyses of data collected in this study will be documented in a SAP, which will be dated, filed, and maintained by the sponsor. The SAP may modify the plans outlined in the protocol; any major modifications of primary endpoint definitions or their analyses would be reflected in a protocol amendment.

Statistical analyses will be performed using statistical software packages including SAS and Stata. All tests will be two-tailed, and the level of significance will be set at α =0.05. Statistical tests will only be conducted if the sample size is adequate for comparisons. The analytical plan for each study objective is described in this section. Study objectives are listed in italic font for reference.

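### The precision in Table 9.5.1 assumes independent patients, but Phases 3 to 4b draw them from about 15 providers at most, so it is optimistic for any positive within-provider correlation

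*Protocol*

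**What the plan says.** Protocol section 9.5 states that a sample size calculation does not apply and presents "Table 9.5.1 Standard Error around a Point Estimate", which gives a plus-or-minus figure by sample size (30 to 300) and percentage. The same section reports the feasibility result: "Feasibility assessment indicated 11 providers prescribed GLAS to 39 patients and 21 providers prescribing VEN to 86 patients".

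Section 9.1 fixes where patients come from. For Phase 3, "CHSS will invite 15 providers who have indicated previously treating a patient with GLAS to participate in Phase 3". The abstract confines the Phase 4 glasdegib expansion to the Phase 3 providers, and Phase 4b will "collect data for VEN-treated patients from those initial providers who participated in Phase 3 data collection". On size, "The total proposed sample size across the 2 treatment arms is 150 patients".

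The treating physician abstracts the chart (abstract, Data sources), without help from site staff (section 9.6). Table 9.3.1 marks transfusion independence as provider reported and takes response from the provider's report. Section 9.8 plans no random data validation.

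Section 9.7.3 plans medians, landmark proportions and 95% confidence intervals from Kaplan-Meier estimates and life tables. Section 9.7 does not mention provider as a source of correlation. Section 9.9 concedes that purposive sampling limits representativeness but does not mention precision.

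**The concern.** Patients of one physician share that physician's choice of regimen, threshold for stopping treatment, reading of response and habits of abstraction. Their outcomes are then likely to be positively correlated, and n patients carry less information than n independent ones. A precision table indexed by n alone overstates what the study will know.

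This matters because the protocol specifies no a priori hypotheses and its abstract says each cohort will be described independently. The estimates and their intervals are the main product. An interval labelled 95% that covers less often than that would misstate the evidence on response, transfusion independence and survival.

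**Working it through.** **Step 1. Reproduce the table.** Half-width = 1.96*sqrt(p(1-p)/n). At p = 50%:
- n = 30: 1.96*sqrt(0.25/30) = 17.9 points
- n = 100: 1.96*sqrt(0.25/100) = 9.8 points
- n = 300: 1.96*sqrt(0.25/300) = 5.7 points

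All 30 cells agree to within 0.05 points. The entries are thus 95% half-widths, not standard errors as titled (the standard error at n = 100, p = 50% is 5.0 points). They contain no design effect.

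**Step 2. Cluster sizes from the protocol's counts.** m = patients / providers.
- Glasdegib, 39 patients: 39/15 = 2.6 with the 15 invited providers, or 39/11 = 3.5 with the 11 prescribers found at feasibility.
- Venetoclax at the feasibility rate: 86/21 = 4.1 per provider, so 15 providers give about 61 patients.
- Venetoclax filling the cap: 150 - 39 = 111 patients, 111/15 = 7.4. This is a ceiling.

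**Step 3. Design effect.** DE = 1 + (m - 1)*ICC, with equal clusters. The adjusted half-width is the naive one times sqrt(DE). Coverage of the naive interval is approximately 2*Phi(1.96/sqrt(DE)) - 1. The ICC is not in the documents; 0.02 to 0.10 is an assumed range.

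Example: glasdegib 39/11 at ICC 0.10. DE = 1 + 2.545*0.10 = 1.255, sqrt(DE) = 1.120, and 15.7 points becomes 17.6.

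Results at p = 50%:

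| Cohort | Naive half-width | ICC 0.02 | ICC 0.05 | ICC 0.10 | Coverage at ICC 0.10 |
|---|---|---|---|---|---|
| Glasdegib 39/15 | 15.7 | 15.9 (+2%) | 16.3 (+4%) | 16.9 (+8%) | 93.1% |
| Glasdegib 39/11 | 15.7 | 16.1 (+3%) | 16.7 (+6%) | 17.6 (+12%) | 92.0% |
| Venetoclax 61/15 | 12.5 | 12.9 (+3%) | 13.5 (+7%) | 14.3 (+14%) | 91.4% |
| Venetoclax 111/15 | 9.3 | 9.9 (+6%) | 10.7 (+15%) | 11.9 (+28%) | 87.4% |

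**Step 4. Sensitivity.**
- At ICC 0.01 the widening in these four cases is 1 to 3%. It is 4% if 111 venetoclax patients came from 11 providers.
- Unequal clusters increase the effect. With an assumed coefficient of variation of cluster size of 0.6, DE = 1 + (1.36*m - 1)*ICC. At ICC 0.10 the widening becomes 12% (39/15), 18% (39/11), 20% (61/15) and 38% (111/15).
- Phase 4a allows glasdegib patients up to the full 150. From 15 providers that would be m = 10, larger than any venetoclax cluster above.

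**The case against.** The strongest reply is that the variance estimator is normally left to the statistical analysis plan. The protocol defers detailed methodology there, and the plan is not at hand. That stands. A reader might infer that the study's reported 95% intervals will be too narrow. The protocol does not support that: section 9.7.3 names Kaplan-Meier estimates and life tables but no variance method. The statement is firm in direction only for Table 9.5.1, which the protocol itself publishes.

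A reader might also infer severe under-coverage, particularly for venetoclax. This is not supported either. The ICC and the spread of cluster sizes are assumptions, and 111 venetoclax patients is a ceiling. Venetoclax is affected more only if glasdegib stays near 39. The venetoclax cohort is also secondary and optional.

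Other points stand in part:
- Table 9.5.1 is a generic look-up that drives no go/no-go rule, so correcting it changes no stated design decision. It is nevertheless the only precision the protocol gives.
- Eleven providers is a feasibility count, not a design figure, and Phase 5 may add patients without saying from which providers.
- Several outcomes have objective anchors: count thresholds for the types of complete response, a 56-day rule for transfusion independence, and a date of death. Providers are asked to substantiate entries from notes and laboratory results. This may keep the ICC low for some endpoints, but does not make it zero.
- Error shared by one assessor is mainly bias, which a design effect does not repair.

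**Conclusion.** The point holds in a limited form. Table 9.5.1 assumes independence, while the sampling rules for Phases 3 to 4b concentrate patients in about 15 providers at most. Its half-widths are therefore too small for any positive within-provider correlation. The final intervals share the fault only if they are computed without regard to provider.

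The likely effect on the primary glasdegib cohort is small. For venetoclax it ranges from modest at the feasibility rate to material if that cohort fills the cap. These sizes rest on an assumed ICC of 0.02 to 0.10, equal clusters and glasdegib staying near 39 patients. This is a worthwhile and inexpensive improvement, not a flaw that undermines the study.

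**What to change.** In section 9.5, state that the half-widths assume independent patients. Give them at the feasible cohort sizes (for example 39, 61, 86 and 111) with a design-effect range over a stated ICC range.

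In section 9.7, report 95% intervals for proportions and Kaplan-Meier estimates that treat provider as the cluster, by a provider-level bootstrap or a robust variance with a small-sample correction. Show the naive interval beside each. Note that with 11 to 15 clusters the corrected intervals are approximate, and that they do not correct bias from shared assessors.

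The submitting provider is already known for each eCRF, because section 9.8 relies on contacting that provider for validation. No new data are needed. The cost is some protocol wording, a little programming and slightly wider stated precision.

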9.6. Data management

All study data will be entered into the eCRF. The eCRF is designed to allow providers to efficiently move through the patient chart or EMR based on the journey of the patient through the course of their disease. The eCRF conforms to the rules and regulations of the Health Insurance Portability and Accountability Act (HIPAA) of 1996 governing the abstraction and storage of protected health information (PHI). Limited and necessary to achieve study objectives PHI (e.g., treatment date, date of death) will be collected in the course of the chart review or stored in the eCRF.

Physicians will be compensated through an honoraria payment for each completed and validated eCRF. Participating physicians will be asked to complete the chart review individually, meaning that site research staff or supportive staff will not complete any data abstraction.

Cardinal Health will be responsible for the programming, testing, and hosting of data from submitted eCRFs. Providers will access the eCRF through a secure web-based portal, including during the field-testing procedures, with all data stored on encrypted, password protected, and HIPAA compliant servers housed within the Cardinal Health electronic data storage infrastructure. Cardinal Health will perform extensive testing of the eCRF to ensure functionality across web-based user environments, looping logic to ensure proper alignment of data-related fields (required responses to certain fields prior to entering data into subsequent field), and other programmatic checks to ensure the reduction of the input of erroneous data (such as specifying maximums for year of birth or initiation of index treatment within the dates of the enrollment period). In addition, the eCRF will be fieldtested among 4 providers to ensure its functionality, the correct interpretation of the questions in relation to the data points of interest, and the length of time required for completion for a single patient. The pre-test results will be reviewed by Pfizer with Cardinal Health staff; however, Pfizer will not have access to the individual data collected. Any changes made to the eCRF document as a result of the pre-test will require the resubmission of the eCRF and study protocol to the IRB.

9.6.1. CRFs/ Electronic data record

As used in this protocol, the term CRF should be understood to refer to either a paper form or an electronic data record or both, depending on the data collection method used in this study.

A CRF is required and should be completed for each included patient. The completed original CRFs are the sole property of Pfizer and should not be made available in any form to third parties, except for authorized representatives of Pfizer or appropriate regulatory authorities, without written permission from Pfizer. The investigator shall ensure that the CRFs are securely stored at the study site in encrypted electronic form and will be password protected to prevent access by unauthorized third parties.

The investigator has ultimate responsibility for the collection and reporting of all clinical, safety, and laboratory data entered on the CRFs and any other data collection forms (source documents) and ensuring that they are accurate, authentic/original, attributable, complete, consistent, legible, timely (contemporaneous), enduring, and available when required. The CRFs must be signed by an authorized staff member of the investigator to attest that the data contained on the CRFs are true. Any corrections to entries made in the CRFs or source documents must be dated, initialed, and explained (if necessary) and should not obscure the original entry.

In most cases, the source documents are the hospital or the physician's chart. In these cases, data collected on the CRFs must match those charts. In some cases, the CRF may also serve as the source document. In these cases, a document should be available at Cardinal Health and at Pfizer that clearly identifies those data that will be recorded on the CRF, and for which the CRF will stand as the source document.

9.6.2. Record retention

To enable evaluations and/or inspections/audits from regulatory authorities or Pfizer, the investigator agrees to keep records, including the identity of all participating patients (sufficient information to link records, e.g., CRFs and hospital records), all original signed informed consent documents, copies of all CRFs, safety reporting forms, source documents, detailed records of treatment disposition, and adequate documentation of relevant correspondence (e.g., letters, meeting minutes, and telephone call reports). The records should be retained by the investigator according to local regulations or as specified in clinical study agreement (CSA) whichever is longer. The investigator must ensure that the records continue to be stored securely for so long as they are retained.

If the investigator becomes unable for any reason to continue to retain study records for the required period, (e.g., retirement, relocation), Pfizer should be prospectively notified. The study records must be transferred to a designee acceptable to Pfizer, such as another investigator, another institution, or to an independent third party arranged by Pfizer.

Study records must be kept for a minimum of 15 years after completion or discontinuation of the study or for longer if required by applicable local regulations.

The investigator must obtain Pfizer's written permission before disposing of any records, even if retention requirements have been met.

9.7. Data analysis

9.7.1. Analysis overview

Detailed methodology for summary and statistical analyses of data collected in this study will be documented in a SAP, which will be dated, filed, and maintained by the sponsor. The SAP may modify the plans outlined in the protocol; any major modifications of primary endpoint definitions or their analyses would be reflected in a protocol amendment.

Statistical analyses will be performed using statistical software packages including SAS and Stata. All tests will be two-tailed, and the level of significance will be set at α =0.05. Statistical tests will only be conducted if the sample size is adequate for comparisons. The analytical plan for each study objective is described in this section. Study objectives are listed in italic font for reference.

9.7.2. Analysis of baseline characteristics

Patient demographics and clinical characteristics will be summarized using descriptive statistics for the 2 treatment groups: mean, standard deviation (SD), median, range will be calculated for continuous variables and for categorical data, counts and proportions will be calculated.

Univariate analyses of baseline characteristics will be conducted to compare mean (medians where appropriate) and proportions across treatment groups using t-tests (Wilcoxon where appropriate) and chi-square (Fisher's exact where cell size is fewer than 5).

9.8. Quality control

During data collection, Cardinal Health clinical research staff review all submitted eCRFs for quality control. The Cardinal Health clinical research team will inspect each submitted eCRF for implausible dates (i.e., date of death prior to last date of treatment), non-standard treatments (e.g., treatment regimens unknown to be used for the cancer under study), lab and radiology results which are inconsistent with known clinical parameters, or other clinical data which is inconsistent with known standards and outcomes. In addition to review of the submitted data by the clinical research team, the study statistician will conduct an analysis of submitted data to identify any data points inconsistent (outliers) with the study population average. This analysis will include a descriptive analysis of the provider characteristics, demographics, baseline clinical and disease characteristics, and characteristics of treatment patterns. Data points flagged as outliers will be delivered to the clinical research team.

Should outliers be discovered, Cardinal Health clinical research will contact the provider submitting the eCRF for data validation. All providers are informed in their contractual agreement that follow-up with clinical staff at Cardinal Health may be required. Participating providers are asked to create a 4-digit unique identifier code per patient which is provided to

PFIZER CONFIDENTIAL

Cardinal Health through the eCRF and used for identifying the patient record for validation between Cardinal Health and the provider. Individual eCRFs, which cannot be validated, will be removed from the study dataset. A provider who is unable to validate a data point will only not be compensated for the patient record which was removed. All other data will be considered valid provided additional patients from that provider are not selected for random validation.

As providers will be trained on data collection, no random data validation will be conducted. However, CHSS research analytics will evaluate all reported data points to identify data outliers and providers may be selected to validate their responses for specific patients. Patients for whom the data are deemed questionable by Cardinal Health staff will be excluded; providers will not be compensated for excluded data. No resampling to replace the excluded eCRF will occur. Providers who are non-responsive to any validation request will be removed from the database and all remaining eCRFs from the provider are subject to additional clinical review.

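### Section 9.8 removes whole patient records for one unvalidated data point, or on an undefined staff judgement made with outcomes visible

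*Protocol*

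**What the plan says.** All of this stands in Protocol Section 9.8 (Quality control), unless another section is named.

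- **Clinical review.** Vendor staff inspect every submitted eCRF for impossible dates, unusual regimens, implausible laboratory or radiology results, and "other clinical data which is inconsistent with known standards and outcomes".
- **Statistical screen.** The study statistician is to "identify any data points inconsistent (outliers) with the study population average". The content listed for this analysis is provider characteristics, "demographics, baseline clinical and disease characteristics, and characteristics of treatment patterns". Response and survival are not listed.
- **Wider screen.** A later paragraph goes further: "CHSS research analytics will evaluate all reported data points to identify data outliers". Table 9.3.1 (Section 9.3) shows that the reported data include response, relapse, transfusion dates and date of death.
- **Query step.** "Should outliers be discovered, Cardinal Health clinical research will contact the provider submitting the eCRF for data validation".
- **First removal route.** "Individual eCRFs, which cannot be validated, will be removed from the study dataset". The compensation sentence that follows makes clear that the trigger is a data point the provider cannot validate, and that what is removed is the patient record.
- **Second removal route.** "Patients for whom the data are deemed questionable by Cardinal Health staff will be excluded".
- **No replacement.** "No resampling to replace the excluded eCRF will occur".
- **Random validation.** One sentence treats a provider's other data as valid unless further patients are chosen for random validation. A later sentence says that none will be done.

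Section 9.9 (Strengths and weaknesses) does not mention these exclusions.

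**The concern.** The unit of removal does not match the unit of doubt. One laboratory value that cannot be confirmed takes the patient's usable OS, EFS and response data out of the study as well.

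The second route is looser. *Questionable* is not defined, and the sentence does not require that a query was sent or failed. The people who decide can see outcomes, and one of their review criteria is disagreement with known outcomes. Section 9.1 says that the vendor does not receive the medical record, so staff cannot settle a doubt from the chart. The judgement rests on the eCRF and the provider's reply.

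Section 8 justifies the study by the limited documentation of outcomes on these drugs. A rule that can drop records because they disagree with known outcomes works against that purpose. What is at stake is selection related to outcome in the Kaplan-Meier medians, landmark proportions and response rates that Section 9.7.3 plans, in a glasdegib cohort that may be small. Section 9.5 reports 39 glasdegib patients at feasibility. Phase 3 has 15 patients, where one record is 1/15 = 6.7 percentage points of any proportion, and those results inform the decision to continue (Section 9.1).

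**Working it through.** **1. The plan's own precision figures.** Table 9.5.1 reproduces as 95% half-widths, 1.96 × √(p(1 − p)/n). For p = 0.5 and n = 30: 1.96 × √(0.25/30) = 17.9 points, as printed. All 30 cells agree to within 0.1 point. The point disputes none of them.

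**2. Loss of precision from removals.** At p = 0.5 the half-width is 1.96 × √(0.25/39) = 15.7 points for n = 39, and 1.96 × √(0.25/35) = 16.6 points for n = 35. This is minor, so the issue is bias.

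**3. Illustration for survival.** Inputs: n = 39 (Section 9.5); median OS 8.3 months (a figure printed in Section 7, in a sentence that is incomplete, so used here only as an assumption); exponential survival; no censoring; the k records lost all come from one tail. The number of records that will be removed is not in the protocol, so k is assumed.

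- True 12-month survival: S = exp(−ln 2 × 12/8.3) = 0.367, or 39 × 0.367 = 14.3 patients.
- k longest survivors lost: (14.3 − k)/(39 − k).
- k shortest survivors lost: 14.3/(39 − k).

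By hand this gives 33.3% (2 longest lost), 29.5% (4 longest) and 40.9% (4 shortest). The 20,000 simulated cohorts agree to within 0.1 point and also give the mean sample median:

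| Records lost (of 39) | 12-month survival | Median OS, months |
|---|---|---|
| None | 36.7% | 8.45 |
| 2 longest | 33.2% | 7.85 |
| 4 longest | 29.4% | 7.28 |
| 2 shortest | 38.6% | 9.08 |
| 4 shortest | 40.8% | 9.74 |

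**4. Range over the assumed median.** With a true median of 6 months, 12-month survival is 25.0% with no loss, 16.4% without the 4 longest and 27.8% without the 4 shortest. With 12 months the figures are 50.0%, 44.3% and 55.7%.

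**5. Cohort size.** With a median of 8.3 months, losing the longest-surviving 10% or so gives 29.4% at n = 39 (4 lost), 29.3% at n = 86 (9 lost) and 29.6% at n = 150 (15 lost). The shift depends on the share removed, so a larger cohort does not cure it.

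**6. Response.** With an assumed 12/39 = 30.8%, losing 4 responders gives 8/35 = 22.9%, and losing 4 non-responders gives 12/35 = 34.3%.

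**The case against.** The best defence is the query step. An outlier does not delete a record; it goes to the treating physician, who holds the chart. A true long survivor or late responder can be confirmed and kept. Because the vendor never sees the chart, dropping a record that nobody can confirm is a defensible integrity safeguard. This stands for the first route, except that it does not explain why confirmed fields must go with the unconfirmed one. It does not cover the second route, whose sentence follows one about selecting providers for validation but is not tied to the result.

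Four stronger readings are tempting, and the protocol does not support them:

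- *Survival is screened against the study average.* The average-based analysis does not list response or survival. That outcomes are in view follows from the screen of all data points and the check against known outcomes, with no masking described.
- *Only atypical records are ever challenged.* Every eCRF is inspected for date and value errors. Sections 9.2.1 and 9.6 add automatic checks, and Section 9.1.1 has staff observe each provider's first abstraction.
- *Extreme outcomes will be trimmed towards the average.* This is a risk and not a stated plan. The illustration moves in either direction and assumes the worst case of one-tail loss.
- *Confidence intervals become too narrow.* The half-width at 50% widens slightly, from 15.7 to 16.6 points.

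It can also be said that removal counts and sensitivity analyses belong in the SAP. That is usual, but the deletion rule itself is fixed in the protocol and acts during data collection. A later plan can analyse removed records only if they have been retained.

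Finally, full masking to survival would clash with the check that death does not precede last treatment. That is a fair limit on the remedy.

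**Conclusion.** The point holds as a badly fixed exclusion rule. Whole records go for one unvalidated data point, and a second, undefined ground lets staff exclude patients with outcomes visible and no stated failed query. Usable outcome data are discarded without need, and the records lost are unlikely to be a random subset.

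The size and direction of any bias cannot be known from the protocol. Under the stated assumptions (39 patients, median 8.3 months, exponential survival, no censoring, one-tail loss of 2 to 4 records), 12-month survival moves by about 2 to 7 points and median OS by about 0.6 to 1.3 months. These are extreme cases for the number removed; if few queries fail, the effect will be smaller. The change is worth making because it is cheap.

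**What to change.** Reword Section 9.8 as follows:

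1. Keep every value that the provider confirms, however extreme.
2. Set only the unverifiable field to missing and keep the patient.
3. Limit whole-record removal to objective grounds: proven ineligibility, a duplicate, or a chart that cannot be traced. Ineligibility includes an unverifiable item that eligibility depends on, such as the date of death required by inclusion criterion 4 for patients with under 6 months of follow-up. Decide each removal before outcome analysis.
4. Delete the questionable-data ground, or define it and make it conditional on a failed validation.
5. Reconcile the two statements on random validation.
6. Report the number of removals by cohort and reason.
7. Retain the removed eCRFs and run one sensitivity analysis on all eligible submitted eCRFs.

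The cost is a rewording, a few missing fields in place of a fully clean dataset, and one extra analysis.
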